# **Physical Exercise Training to Enhance Executive and Social Functions**

**May 17th, 2021**

## **Statistical Analysis Plan and Preliminary Results**

**Hypothesis:** PE is predicted to be effective in reducing the EF and social impairments in these adolescents.

**Statistical Analysis:** Repeated measure ANOVA using SPSS ( is a software package used for interactive, or batched, statistical analysis) are performed to test the effectiveness of PE on social functions and EF in low and high autistic groups.

**Preliminary Results:** Reduced aggression for both autistic groups was found in the intervention when compared to control. Worse empathy in the intervention group when compared to the controls in both autistic groups.

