Given EF impairments along with social function deficits are found in the sub-clinical individuals with BAP (Hill, 2004), is the training pertaining to ASD applicable to these individuals? In prior literature, physical exercise (PE) has been proved to enhance EF (Best, 2010) and social functions (Sowa & Meulenbroek, 2012). For instance, regular PE can enhance cerebral blood flow and increase the formation of new blood vessels in a number of brain regions that are involved in EF and social functions (e.g., Colcombe & Kramer, 2003). More specifically, PE is shown to enhance the performance of EF in healthy children and pre-adolescents (Best, 2010) and those with ASD (Lang et al., 2010). For example, Lang et al. (2010) and Lochbaum and Crews (2003) found that PE including jogging significantly decreased the repetitive and off-task behaviors and the level of aggression in individuals with ASD. Nevertheless, although PE is shown to be beneficial to reduce the symptoms and EF as well as social impairments in ASD, whether it produces the same positive outcomes on enhancing EF and social functions in the non-clinical population remains to be answered.

To address the research questions listed above, this proposed study aims to investigate whether PE training enhances the EF and social functions in the adolescents with BAP.

Research plan and methodology

Participants

To detect possible differences between the means of the primary measure with a power of 80%, eighty adolescents from secondary schools in Hong Kong and Australia will be recruited in this study (Hopkins et al., 2009). Written informed consent will be obtained from all participants. For participants who are below 18 years old, the consent from their parents or guardians will be obtained. Based on their self-reported autistic traits measured by Autism- Spectrum Quotient- Adolescent Version (details listed below), they will be categorized into two groups: 1) typically developing group (low ASD traits) and 2) BAP group (high ASD traits). To be included in the study, they must meet the following criteria: a) age ranges from 7 to 20; b) studying at one of the primary and secondary schools in Hong Kong; c) have never been diagnosed with ASD or any other disorder listed in the Fifth Edition of *Diagnostic and Statistical Manual of Mental Disorders* (DSM-V); and d) are not currently under any psychiatric medications or therapies.

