Randomization. This study consists of a double-blind, and randomized controlled trial (RCT). After obtaining the informed consent, participants will be randomized into two conditions (1. physical exercise (PE) training group or 2. control group) using urn randomization, a covariate adaptive randomization method. A trained research assistant or a fitness trainer will be responsible to monitor and ensure the safety of the training process.

Physical exercise training. The PE training will adapt the exercise training employed by Lochbaum & Crews (2003) and Nicholson et al. (2011) since they targeted adolescents with ASD and the protocol of training can easily be replicated. The entire PE training lasts for six weeks and participants need to participate in a total of 12 sessions. In each session, every participant will be trained to run for 30 minutes on a treadmill. According to Exercise and Sports Science Australia (ESSA) exercise intensity guidelines, the intensity of running is suggested to be moderate and vigorous (alternating between the two) in this proposed study.

Control group. Participating adolescents in the control group will not receive any treatments. They are considered as waitlist controls.

Measures

The following self-reported measures will be administered at the baseline, post-training and 1-year follow-up.

Demographics. A simple demographic questionnaire will be used to gather participants personal information, including age, gender, current medication or therapy, and medical history of the participant and his/her family members. Besides, the blood pressure and heart rate of the participants will be assessed by electrocardiogram.

Autistic traits. The Autism-Spectrum Quotient-Adolescent Version (AQ-Adolescent; Baron-Cohen et al., 2006) and related self-report scales will be used to measure ASD traits. The AQ- adolescent is a self-report questionnaire comprising of 50 items assessing five areas, namely social, attention switching, attention to detail, communication and imagination. Participants will be asked to rate each item on a four-point Likert scale. The AQ-Adolescent received an excellent test-retest reliability ($r = .92$; Baron-Cohen et al., 2006) and a good internal consistency ($\alpha = .88$, Sonié et al., 2013).

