Executive functions and social functions. EF and social functions will be measured using the Cambridge Neuropsychological Test Automated Battery (CANTAB). The CANTAB is a computerized test battery targeting multiple neuropsychological functions that has been validated in different cultures (De Luca et al., 2003). This battery includes Reaction Time, Paired Associates Learning, Spatial Working Memory, One Touch Stockings of Cambridge, Multitasking Test, and Emotion Recognition Task. Besides

the CANTAB, participant's psychological well-being including resilience and mental health will be measured.

Implications

Although the benefits of physical exercise have been studied in the ASD, BAP is under studied in prior literature. This proposed study will extend from the current literature to investigate the non-clinical group who have autistic traits with a longitudinal and randomized controlled trial design (RCT). The findings of this proposed study have multiple levels of significance and implications. For instance, if the hypotheses are supported, the PE training which is more cost-effective than psychotherapy in treating EF and social functioning deficits and associated impairments can be promoted to school settings. Ultimately, it can be incorporated to the curriculum of the primary and secondary schools to reduce BAP and associated impairments in the adolescents. Secondly, by examining those with sub-clinical symptoms, this research will contribute to early trainings approaches for the condition. Lastly, this proposed study can also help promote physical activities among adolescents which can further decrease mental and health issues in Hong Kong (MacDonald et al. 2011).

References

Alvarez, J. A., & Emory, E. (2006). Executive function and the frontal lobes: A meta-analytic review. *Neuropsychology Review*, 16(1), 17–42. doi:10.1007/s11065-006-9002-x

American Psychological Association. (2013). *Diagnostic and statistical manual of mental disorders*. Washington, DC: Author.

Anderson, S. W., Bechara, A., Damasio, H., Tranel, D., & Damasio, A. R. (1999). Impairment of social and moral behavior related to early damage in human prefrontal cortex. *Nature Neuroscience*, 2(11), 1032.

Bailey, C. E. (2007). Cognitive accuracy and intelligent executive function in the brain and in business. *Annals of the New York Academy of Sciences*, 1118, 122–141. doi:10.1196/annals.1412.011

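### The SAP's repeated-measures ANOVA names no visits, no effectiveness term and no missing-visit rule; a baseline-adjusted arm difference at post-training would be explicit, usually more precise, and keep more of the data

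*SAP*

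**What the plan says.** The SAP's Statistical Analysis statement is one sentence. It gives the method as "Repeated measure ANOVA using SPSS" and says that these analyses "are performed to test the effectiveness of PE on social functions and EF in low and high autistic groups". It names no factors, covariates, contrast, sphericity rule or missing-data rule.

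The protocol has no analysis section. What it does supply is this:

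- Measures: "The following self-reported measures will be administered at the baseline, post-training and 1-year follow-up". The executive and social outcomes come from a computerised battery (CANTAB), described under the same heading but not itself self-reported.
- Participants: the trial is sized to detect "differences between the means of the primary measure with a power of 80%, eighty adolescents". Effect size, SD and alpha are not given. On autistic traits, "they will be categorized into two groups", low and high.
- Randomization: two arms, by a covariate-adaptive urn method whose covariates are not listed.
- Control group: no treatment. "They are considered as waitlist controls", with no statement of whether or when they are trained.

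The SAP also reports preliminary between-arm findings: lower aggression but worse empathy in the intervention group.

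**The concern.** Repeated-measures ANOVA yields several tests, and the SAP does not say which one answers the hypothesis. The candidates include the arm main effect, arm-by-time over two or three visits, arm-by-time-by-trait group, and separate analyses by trait group. They ask different questions and differ in power.

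Three consequences follow.

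1. If baseline and post-training enter, arm-by-time compares change scores. The baseline is then subtracted in full rather than given the weight the data support, which costs precision unless the visits are highly correlated.
2. If all three visits enter, arm-by-time has 2 df. A significant result does not say when or in which direction the arms differ, and it is not the difference between means on which the trial was sized. Direction matters here, because the preliminary results point in favourable and unfavourable directions for different outcomes.
3. Classical three-visit ANOVA needs complete rows. A participant seen at baseline and post-training but not at 1 year is lost from the post-training comparison too.

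**Working it through.** **Inputs.** From the documents: 80 participants, 80% power, two arms, two trait groups, three visits. Assumed, because neither document gives them: 40 per arm, two-sided 0.05, SD 1 at every visit, equal correlation rho between visits, no missing data unless stated. The one reliability coefficient in the protocol (.92) belongs to the autistic-traits questionnaire and is not an outcome correlation.

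**The plan's own figure.** N = 80 cannot be reproduced without an effect size, SD and alpha. Solving backwards for a simple comparison of two means gives (1.960 + 0.842) × √(2/40) = 0.626 SD, or 0.634 SD by the noncentral t: about 0.63 SD.

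**Two visits.**
- Change score: variance 2(1 − rho), 78 df.
- Baseline-adjusted: variance 1 − rho², 77 df.
- Ratio: 2(1 − rho)/(1 − rho²) = 2/(1 + rho).

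At rho 0.6 the variances are 0.80 and 0.64, a ratio of 1.25. The 95% CI half-widths are 1.99 × √(2 × 0.80/40) = 0.40 SD and 1.99 × √(2 × 0.64/40) = 0.36 SD.

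**Three visits, arm-by-time.** Noncentral F on 2 and 156 df, with noncentrality (40/2) × Σ(δ − mean δ)²/(1 − rho), where δ is the arm difference at each visit. At rho 0.6 and 0.5 SD at post-training:
- effect sustained at 1 year, δ = (0, 0.5, 0.5): 20 × 0.1667/0.4 = 8.33
- effect gone, δ = (0, 0.5, 0): again 8.33
- effect halved, δ = (0, 0.5, 0.25): 20 × 0.125/0.4 = 6.25

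The test has the same power whether the effect lasts or vanishes, so it cannot tell these apart.

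**Power at 0.5 SD, complete data**

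| rho | Change score | Three visits, sustained or gone | Three visits, halved | Baseline-adjusted, post-training |
|---|---|---|---|---|
| 0.3 | 46% | 47% | 37% | 64% |
| 0.5 | 60% | 62% | 50% | 72% |
| 0.6 | 69% | 73% | 59% | 79% |
| 0.7 | 81% | 85% | 73% | 87% |
| 0.8 | 94% | 96% | 89% | 96% |

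At rho 0.9 all are above 99%. Against the three-visit test with a sustained or vanished effect, the gain disappears at rho 0.78. At the implied 0.63 SD and rho 0.6, the change score has 88% and baseline adjustment 94%.

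**Other readings of the same sentence.** At rho 0.6 and a sustained 0.5 SD effect, the arm main effect has about 40% power over three visits and 23% over baseline and post-training, because the baseline visit dilutes the difference.

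**Missing only the 1-year visit.** If 20% do so, complete-case ANOVA has 32 per arm. At rho 0.6, three-visit power falls from 73% to 62%, or from 59% to 49% if the effect is halved. The baseline-adjusted post-training comparison keeps those participants and stays at 79%.

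**Sphericity.** Six weeks and one year are unequal gaps, so equal correlation is doubtful. With assumed correlations of 0.8 between the first two visits and 0.4 for the other pairs, the uncorrected three-visit F rejected a true null about 6.5% of the time in simulation, against a nominal 5%.

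**Within one trait group** (20 per arm if split evenly, rho 0.6, 0.5 SD): 49% against 41% power, with half-widths of 0.51 and 0.57 SD. These support estimates, not powered tests.

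**The case against.** The strongest reply is that visits and term could both be named inside the existing ANOVA. That is right, and part of the three-visit shortfall comes from the unnamed contrast rather than from ANOVA. At rho 0.6 and 0.5 SD, a planned contrast of the later visits against baseline has 81% power if the effect is sustained, slightly above the 79% proposed. It falls to 57% if the effect is halved at 1 year and 30% if it is gone.

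A reader might infer that an elaborate mixed model is required. The figures do not support that: the gain comes from baseline adjustment, which ordinary ANCOVA delivers. Nor does a mixed model settle missing data by itself. It still assumes missing at random, and participants without a baseline drop out unless a rule is stated.

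Three further objections stand:
- The size of the gain rests on assumed inputs, and it is smaller at the implied 0.63 SD than at 0.5 SD.
- The schedule sentence speaks of self-reported measures, so three CANTAB visits are a reasonable inference from the shared heading, to be confirmed.
- Between-arm results have been seen, so changing the test now adds analytic freedom and must be disclosed.

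**Conclusion.** The specification gap is certain: visits, term and missing-visit rule are absent from both documents. The advantage of naming a baseline-adjusted post-training difference is real but conditional. With 40 per arm, two-sided 0.05, equal correlation and complete data, at rho 0.6 it is 79% against 69% for the change score at 0.5 SD, or 94% against 88% at about 0.63 SD. It is larger at lower rho, and little or nothing at about 0.8 or above. Keeping participants who miss only the 1-year visit is a separate benefit.

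A reader might conclude that the planned ANOVA is invalid or biased. The documents do not support that. With complete data, the change-score test is valid under randomisation, and so is the three-visit test if sphericity holds or a correction is applied. Bias would need outcome-related dropout, and the documents report no dropout at all. Nor do they show that waitlist controls were trained before the 1-year visit; they are silent, so the meaning of that contrast is open. The change is worth making as an improvement in precision and data use, held with moderate confidence.

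**What to change.** Add to the SAP, for each outcome:

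- **Effectiveness test.** The arm difference at post-training, with 95% CI, adjusted for baseline, trait group and the urn randomisation covariates, which must be listed. Use ANCOVA or, to the same end, a mixed model with post-training and 1-year values as outcomes and unstructured covariance.
- **Who is included.** Everyone with a post-training value, in the arm to which they were randomised. State a rule for a missing baseline, for example mean imputation of the baseline covariate, and report by arm how many have no post-baseline value.
- **Trait groups.** Arm differences in the low and high groups through an arm-by-trait-group term, reported as estimates.
- **1-year visit.** Confirm that CANTAB is given then. Report the contrast separately, and read it as exercise versus no exercise only if the documents confirm that controls were still untrained.
- **Transparency.** Report the SAP's ANOVA alongside, with its visits, term and sphericity correction stated. Label the change as made after the preliminary results.

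The cost is SAP text and a standard model on data already planned; nothing new is collected. The downsides are a missing-at-random assumption and a disclosed post-hoc change. The primary outcome and multiplicity are not settled by this and need their own statement.

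### The trial is powered on a primary measure that neither document names, and the SAP, which already reports two results by arm, sets no primary outcome or error control for executive and social functions

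*SAP*

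**What the plan says.** **Sample size.** The protocol's Participants section opens its justification of eighty adolescents with "To detect possible differences between the means of the primary measure with a power of 80" per cent. This is the only mention of a primary measure in either document.

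**Aim and hypothesis.** The protocol "aims to investigate whether PE training enhances the EF and social functions in the adolescents with BAP". The SAP's hypothesis is that "PE is predicted to be effective in reducing the EF and social impairments in these adolescents".

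**Measurement.** The protocol's section on executive and social functions assigns both domains to CANTAB and names six tasks: Reaction Time, Paired Associates Learning, Spatial Working Memory, One Touch Stockings of Cambridge, Multitasking Test and Emotion Recognition Task. None is ranked. Resilience and mental health are added without an instrument. The Measures section opens with "The following self-reported measures will be administered at the baseline, post-training and 1-year follow-up", which gives three occasions and marks none as decisive.

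**Analysis.** The SAP's whole analysis statement is that repeated measures ANOVAs "are performed to test the effectiveness of PE on social functions and EF in low and high autistic groups".

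**Results already in the plan.** The SAP is headed "Statistical Analysis Plan and Preliminary Results". It reports "Reduced aggression for both autistic groups was found in the intervention when compared to control" and "Worse empathy in the intervention group when compared to the controls in both autistic groups". It gives no instrument, time point, sample size, estimate or interval for either. Both documents are dated 17 May 2021.

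**The concern.** An unnamed primary outcome is a gap in any plan. It matters more here because at least some comparisons by arm had been made by the time of the SAP. Someone following this plan could take any of the six tasks, at either later visit, with the two trait groups pooled, separate or compared by interaction, and present a favourable result as the test of effectiveness. Nothing in the text limits the error of that conclusion, and a reader could not tell a hypothesis that was confirmed from one that was chosen.

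Two consequences follow. The 80% power attaches to no identifiable result. And the SAP does not say whether empathy is a social function, although the reported empathy difference runs against the intervention. If it is one, part of the hypothesised domain already has an adverse result; if it is not, that should have been settled without sight of the result. The protocol's Implications section proposes promoting the training in schools if the hypotheses are supported, so what counts as support needs to be fixed.

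**Working it through.** **1. What is fixed and what is open**

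| Element | Protocol | SAP |
|---|---|---|
| Primary measure | Referred to once, not named | Not mentioned |
| EF and social outcomes | Six named CANTAB tasks, unranked | Domains only |
| Time point | Three occasions, none decisive | Not stated |
| Model term | – | Repeated measures ANOVA in two trait groups; pooled, separate or interaction not stated |
| Alpha, multiplicity | Not stated | Not stated |
| Aggression | Background only, as a finding in ASD | Reported by arm |
| Empathy | Not named | Reported by arm |

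**2. The plan's own figure.** N = 80 can be neither confirmed nor refuted, because only N and power are given. Assuming two-sided 0.05, 40 per arm and no dropout, the standardised difference that 80 participants detect with 80% power is (1.960 + 0.842) × √(2/40) = 0.626 by the normal approximation, or 0.634 by the t distribution. This d is solved back from N. It is not the sponsor's stated effect.

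**3. Error if any favourable task is enough.** Assumed: six tests, one score per task, each at two-sided 0.05, no true effect, and one favourable result sufficing.

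- Favourable direction, independent: 1 − 0.975^6 = 0.141.
- Either direction, independent: 1 − 0.95^6 = 0.265.
- With equal correlation r, favourable direction: 1 − ∫ φ(u) Φ((1.96 − √r·u)/√(1 − r))^6 du. The two-sided version replaces Φ by the probability of lying within ±1.96.

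| Inter-test correlation | False favourable (one test: 2.5%) | False in either direction (one test: 5%) |
|---|---|---|
| 0 | 14% | 26% |
| 0.3 | 12% | 24% |
| 0.5 | 10% | 21% |
| 0.7 | 8% | 16% |

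The middle column matches the harm described, a false claim of benefit. Separate testing by visit or trait group would raise the figures, but the documents do not say that this would be done.

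**4. Power cost of error control.** For d = 0.634 on one given task by a two-sample t-test, the noncentrality is 0.634 × √(n/2) for n per arm.

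- 40 per arm: noncentrality 2.835. Power is 80% at 0.05 (critical value 1.991) and 55% at the first Holm step, 0.05/6 = 0.0083 (critical value 2.707).
- 20 per arm, if the high-trait (BAP) group is half the sample: noncentrality 2.005. Power is 50% at 0.05 (critical value 2.024).

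**The case against.** The best defence is that the results are labelled preliminary and that the plan is not empty. It names a method, two trait groups and a hypothesis limited to two domains. Aggression has some rationale, since the protocol's background cites exercise lowering it in ASD. The unspecified additional self-report scales, the well-being measures or the eyes task in Appendix 1 could be the source of either result, and an earlier dated version of the plan may exist. The hypothesis could also be read as requiring gains in both domains, in which case one favourable task would not suffice and, with no true effect on any task, the error would be smaller than shown.

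Much of this stands as a limit on what can be said. Background rationale is not prespecification, and no link from either outcome to an instrument is stated, but the documents do not exclude planning. The population and model are partly described; what is missing is how the trait groups enter and which term decides. None of it supplies a primary measure or a decision rule.

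A reader might infer more than the text supports:

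- **That the two results are chance findings, or were selected.** The documents do not say how many outcomes were compared, so the figures above do not apply to these results.
- **That CANTAB has already been compared by arm.** No CANTAB result is reported.
- **That the plan was written to fit the results.** A shared date shows no sequence; it only means that neither document is shown to predate them.
- **That the chance of a false claim of benefit is 26%.** That figure counts errors in both directions; the favourable-direction figure is 14%.
- **That 80 participants is the wrong number.** The inputs needed to judge it are absent.

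**Conclusion.** The concern holds. The power statement refers to an unidentified measure, the hypothesis covers two domains with six unranked tasks, nothing decisive is fixed, and the document that should fix it already contains two arm comparisons on outcomes not named under Measures. This needs correction before any confirmatory claim.

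The size is illustrative: roughly three to six times the nominal 2.5% for a false favourable result (8% to 14%). It rests on six tests at an assumed two-sided 0.05, one score each, correlations from 0.7 down to 0, and a rule, not stated in either document, that any one task is enough. The textual finding does not depend on these assumptions. Whether aggression and empathy were planned, and whether CANTAB had been compared by arm, only the sponsor can say.

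**What to change.** Change the SAP, and one sentence of the protocol, as follows.

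1. State which outcomes, participants and time points had been compared by arm when the plan was written.
2. Label aggression and empathy exploratory unless a dated earlier record shows that they were planned. State whether empathy counts as a social function. Report both results, including the adverse one, with instrument, time point, estimate and 95% confidence interval.
3. If a record from before any arm comparison identifies the primary measure, name it. Otherwise fix one score per CANTAB task, one time point, one arm-by-time contrast and the way the two trait groups enter the model. These should be chosen by someone who has seen no arm results, including those for aggression and empathy. Control error over all six tasks with Holm's procedure, so that both EF and social functions are tested, and report all six whatever the result. If a single task is named as primary instead, limit the confirmatory conclusion to that task's domain.
4. Restate the power sentence under Participants for the chosen measure, alpha and population, or remove the 80% claim.

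The cost is text and a less favourable power figure. Under the assumptions in the working, power for one given task falls from 80% to about 55% at the first Holm step in all 80 participants, and to about 50% at 0.05 if the confirmatory test is confined to a BAP half of 20 per arm. No added enrolment is proposed.
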